4.3 Sampling Frame

The sampling frame for this survey will be based on the 2012 Tanzania Population and Housing Census for the Morogoro region. A list of census enumeration areas (EAs) is available with basic housing and population information. Table 2 shows the distribution of households and number of EAs from the sampling frame.

4.4 Sampling Procedure and Sample Allocation

This is a cross-sectional household-based survey with a sample size of 1170 non-pregnant women of reproductive age. The Morogoro region encompasses seven districts, and 45 clusters will be selected from all districts (20 from urban strata and 25 from rural strata).

Data from the 2012 Tanzania Population and Housing Census for the Morogoro region (Table 2) will provide the sampling frame for this survey. Because regional differences in the distribution of rural compared with urban populations in the region, a stratified, multistage probability sample will be used for urban and rural areas. This survey will allow for independent estimates for WRA (Henderson & Sundaresan, 1982). The first stage of the sample design will be the selection of enumeration areas (EA) with probability proportional to size (PPS) design (20 urban and 25 rural areas) (Lemeshow & Robinson, 1985). The Probability Proportional to Size (PPS) design will ensure proper representation by district and population distribution. In the second stage, 26 households will be selected from each EA (totaling 1170 women). To select the households, household listing and maps of their location will be conducted in all the selected EAs prior to the initiation of survey data collection. A household listing form will be used to identify and select eligible households. A two-member team, comprising one mapper and one lister, will visit each EA to locate and mark its physical boundaries. The mapping team will do a census of all households and prepare a list of households with the name of the head and address or location of each household. During household listing, a list of household members, including the individual who prepares and/or purchases food for the household and WRA between 15 - 49years of age. In order to ensure that the household listing is current and to minimize nonresponse, the time period between household listing and the start of data collection will not exceed one month. Only one WRA participant per household will be selected.

The survey findings will be generalizable to the Morogoro region.

Table 2: Distribution of Morogoro región households, number of EAs by district and by type of residence (Census 2012).

District	Number	of Househo	olds	Number	of EAs	
	Rural	Urban	Total	Rural	Urban	Total
Kilosa	71836	30079	101915	762	358	1120
Morogoro	2328	73019	75345	24	688	712
Municipal						
Morogoro Rural	70369	3021	73390	756	30	786
Kilombero	64095	22553	86648	606	189	795
Mvomero	63178	8471	71649	428	78	506
Gairo	32019	4988	37007	307	44	351
Ulanga	45628	7599	53227	684	71	755
Total (%)	349453	149730	499183	3567	1458	5025
	(70%)	(30%)	(100%)	(70.1%	(29.9%)	

The survey manager will number the houses where WRA reside and then divide the number of houses in the EA by the number of households that are to be interviewed in the cluster in order to systematically select the households within the cluster (26 households to be selected per EA). The survey team will use a random number generator to select a random starting point of the sampling and then will select every nth household. If the household meets the eligibility criteria, an eligible woman from the household will be interviewed. If a household includes multiple eligible women, then one woman will be selected randomly to participate.

The survey findings will be reflective of the Morogoro region. A spreadsheet containing all sampling parameters and selection probabilities will be constructed to facilitate the calculation of sampling weights. Sampling weights will be further adjusted for household non-response and as well as for individual non-response. Several sets of weight will be calculated: one set for the households, one set for women individual interview and one for women blood drawing. The final weights will be normalized in order to give the total number of un-weighted cases equal to the total number of weighted cases at regional level, for both household weights and individual weights.

4.5 Data Collection Procedures

Prior to data collection, all field workers (supervisors, team leaders, interviewers, and phlebotomist and lab technicians) will participate in a one-week training on proper data and specimen collection. The training will consist of two days of theoretical training and 3 days on data collection procedures, instruments, and equipment. As part of the role-play, phlebotomist will draw blood specimens from field workers, and laboratory technicians will practice processing and labelling samples. At the end of the training, a written test will be administered to team members. As more trainees will be recruited than those needed, only the best performing individuals will be selected for actual data collection, and the best performing and most experienced interviewers will be hired as team leads. Following the classroom training a week of field pilot testing in 2 to 4 EAs (2 urban and 2 urban and rural EAs) not included in our selected EAs will be conducted to familiarize teams with logistical procedures, field dynamics, and real world scenarios.

• Household and Non-Pregnant Women of Reproductive Age Interviews

The Morogoro Biomarker Survey will collect information from individuals who prepare OR purchase food for household to gather information on general characteristics of the population and their household. Also, information will be collected on maize and wheat flour consumption. The household roster information will collect information on all household residents (including WRA) who share a common kitchen. Information about pregnancy status will be collected for each listed WRA house resident. Small amount of sample wheat and/or maize flour consumed by the household will be collected for analysis at TFNC laboratory as part of fortification assessment. One non-pregnant WRA will be selected to participate in the women questionnaire and blood drawing. The WRA selected will be asked about her medical and pregnancy status and history, and micronutrient supplementation and prescription drug intake. The information collected by the Morogoro Regional Biomarker Survey will follow the Aday and Andersen model (Aday, 1997; 2006). Information on characteristics include: 1) enabling factors (usual source of care, health insurance, wealth index, prenatal care, periconception care, enrollment in government programs, etc.); and 2) predisposing factors, such as woman's age, respondent's education.

Women selected to participate in the sample will be asked to provide informed consent (prior to the blood collection for measurement of biomarkers. For women of reproductive age, blood samples (5-6 mL and 5-6 mL EDTA whole blood) will be collected via venipuncture, and blood tubes will be transported in a cool box to a regional laboratory that will process the specimens within 4 hours of collection.

• Blood collection and processing

Trained phlebotomist will collect 10-12 mL of blood by antecubital venipuncture in certified tubes containing anticoagulant. Due to the nature of the survey, blood samples will be taken in non-fasting conditions. Whole blood with EDTA anticoagulant and non-anti-coagulated whole blood vacutainers well be maintained at 4-8oC for a number of hours and sent to the field laboratory. Upon arrival in the field laboratory whole blood with EDTA anticoagulant will be analyzed by hematology analyzer for determination of hemoglobin and hematocrit. A portion of this blood samples will be separated into serum, plasma, and whole blood and for preparation of aliquots for laboratory processing. A small portion of the EDTA blood will be diluted with ascorbic acid to make red blood cell lysate (1:11 dilution) for determination of RBC folate. The non-anti-coagulated whole blood will be centrifuged after allowing to clot at room temperature for about 30 minutes. After centrifugation, serum will be aliquoted for retinol, Vitamin B12, serum folate, ferritin, soluble transferrin receptor, C - reactive protein, alpha 1 glycoprotein, retinol binding protein. Serum will be then stored at -20oC until shipped to the central lab at TFNC. After samples are received at the central lab, they should be stored at -80 oC until TFNC and/or other labs will conduct biochemical analyses. Detailed procedures for sample collection, shipment, processing and storage are provided in field and laboratory protocol provided in Appendix 8.3.

4.6 Data management and analysis

Data from the Morogoro Region Micronutrient Household and Biomarker Survey will be analyzed in SAS 9.4. Sampling weights will be applied and prevalence estimates will be calculated. Free text data will be translated into English and coded into categories before being analyzed.

Analysis and Statistical methods

The basic analysis is aimed at identifying the number of selected women of reproductive age with anemia, folate or vitamin deficiency, ferritin and retinol deficiency. Participants will be classified deficient based on each biomarker cut-off (Table 3).

Outcome Measures and Analysis

Descriptive analysis will include frequencies, mean and geometric mean values for each biomarker. In addition, for each biomarker prevalence will be determined with 95% confidence intervals. Risk factor analysis will be carried out to determine prevalence risk ratios (PRR), and 95% confidence intervals (CI) for single and combined deficiencies. Significance will be determined for contingency tables by Wald's X2 test. In addition, bivariate and stratified analyses will be performed to examine the association between independent variables and deficiency status and potential confounding and interaction effects. Independent variables that are significantly associated with deficiency status in bivariate analyses will be included in logistic regression models to determine the relative contribution of health services and access factors controlling for other factors. Independent variables will be analyzed as categorical variables. Potential multi-co-linearity among variables will be examined. Continuous outcome variables analysis will be also carried out.

Biomarker indicators

Biomarkers are biochemical, functional or clinical indices of an individual's nutrient intake, status or functional effects. They are required to support evidence-based clinical guidance for health programs and policies for nutrition and health of a population. These indices can reveal information about biological or physiological responses to dietary and behavior or pathogenic processes, as well as can be used to monitor responses to therapeutic interventions and to provide information on inter-individual differences in response to diet and nutrition.

Laboratory assessment of these biomarkers is not only used to detect subclinical deficiency states, but also to confirm clinical diagnosis. Biomarkers have become important with the growing importance of preventive medicine because they provide an objective means of assessment of nutritional status of an individual. These procedures can supplement other methods of nutritional assessment resulting in identification of specific nutritional problems and deficiencies. A nutritional biomarker can be any biological specimen that is an indicator of nutritional status with respect to intake or metabolism of dietary constituents. The biomarkers to be assessed in this study include a full blood count for hemoglobin and hematocrit as well as serum B12, serum and red blood cell folate, Ferritin, Vitamin A, sTfR, CRP and AGP, homocysteine and MTHFR. Table 3 provides summary of the biochemical indicators and analyses for these biomarkers. Detailed laboratory procedures (SOP) for analyses done under TFNC laboratory are provided in Field and laboratory protocol in **Appendix 8.3.** Any sample

shipment to the laboratories outside the country will be done as per signed material transfer agreement (MTA).

Indicator Group	Indicator	Methodology	Cut-off
Anemia	Hemoglobin		Total: < 12.0 g/dL Mild: 11.0-11.9 g/dL Moderate: 8.0-10.9 g/dL Severe: <8.0 g/dL
Inflammatory biomarkers	C-reactive protein	C-reactive protein and α–1 acid glycoprotein-ELISA ¹	
	Alpha-1 Glycoprotein	C-reactive protein and α -1 acid glycoprotein-ELISA ¹	>1 mg/L
Micronutrients	Ferritin	Ferritin and soluble transferrin receptor- ELISA ¹	Bond method (normal under 10 percentile)
	Serum transferrin receptor	Ferritin and soluble transferrin receptor- ELISA ¹	Bond method (normal under 10 percentile)
	Serum retinol	Modified relative dose response (MRDR)-HPLC ²	<20 ug/dL (≤70 µmol/l)
	Retinol binding protein	Retinol binding protein- ELISA ¹	
	Serum Folate	Microbiologic Assay ³	<7 nmol/L
	Red blood cell folate	Microbiologic Assay	Deficiency: <305 nmol/L Insufficiency: < 748 nmol/L
	Serum B-12	Immunoasay based on electrochemiluminescence	Deficiency: < 148 pmol/L Marginal deficiency: 148- 221 pmol/L
Homocysteine	Vitamin B12 and folate	Immunoassay based on fluorescence polarization	>10 nmol/L
Methylene Tetr Hydrofolate Reductase (MTHFR)	ra Folate/one-carbon		NA

Table 3. Biochemical indicators and analyses methodology

¹Erhard et al., 2004 ²Tanumihardjo et al., 2016 ³Bailey et al., 2015

5 **Ethical Considerations**

Potential risk and benefit

The participants might experience temporary discomfort during the blood drawn. This should not affect how they feel. Trained staff will be drawing blood using sterile techniques and personal protective equipment to protect both the participants and staff. Sometimes a person will bleed or have a bruise where the blood is drawn. There is always a very slight chance of infection but this is unlikely to happen given the precautions that will be in place. Some people may feel dizzy or faint. If the participants are found to be severely anemic, we will notify the participants to the nearest heath center in the community. At any time during the survey, the participants can decide to stop or refuse to continue during both the questionnaire or blood drawn.

The participants' opinions and blood samples will help to inform programmers and decision makers about future nutrition programs that will be used to improve the health of the community and the findings will help inform public health strategies to improve the future nutrition in Tanzania. If the participants are found to be severely anemic, we will notify the participants to the nearest heath center in the community.

Confidentiality

All data collected in the study will be linked by identifiers and will be treated with strict confidentially throughout and beyond the duration of the trial, with identifier-linked data available only to study investigator, Names will be collected in the study only to ensure accountability of the survey team and non-duplication in the data/interviewing; for the purpose of analysis, names will be disposed of study participation, and all associated potential risks and benefits. Data collectors will emphasize the unconditional voluntariness of study participation, the right to discontinue at any point during the study, and the confidential nature of all information that will be collected. Consent forms will specify that participants have the option to deny consent for any or all parts of the study procedures without any objections.

Consent process

A consent document in English or Kiswahili will be provided to potential participants and used by the interviewer as a guide for the verbal explanation of the project. The interviewer will give participants adequate information concerning the study, provide adequate opportunity for participants to consider all options, respond to the participants' questions, ensure that participants have comprehended this information, obtain participants' voluntary agreement to participate, provide a facts sheet with information about the study with a contact number, and continue to provide information as participants or situation requires.

An additional informed consent will be asked to the selected non-pregnant WRA participating in the Women's questionnaire and for the blood assessments for full blood count including hemoglobin and hematocrit as well as B12, folate, Ferritin, Vitamin A, sTfR, CRP and AGP, homocysteine and MTHFR. The results for full blood count including hemoglobin will be reviewed as soon as possible after analysis. Individuals found with hemoglobin levels below designated cut-off points and who are severely anemic will be contacted and referred to nearest health facility for further assessment and treatment.

Potential participants will be informed that their participation is voluntary. Potential benefit and minimum risk of participation in this project will be explained to potential participants with clear

language. Households participating in providing wheat and maize flour (50g each) will be compensated in cash for the flour provided. Choosing not to participate or withdrawal from the participation will in no way impact on individual's relationship with any affiliated institution.

If participants agree to participate in the project, participants will be asked to sign a written consent form before the interviews or surveys.

6 Budget

Household and Biomarker Survey Budget

Budget Category	Amount
Transport	\$ 78,307
Per diem	\$ 131,544
Venue	\$ 3,913
Communications	\$ 5,043
Stationary	\$ 2,748
Disposable Supplies	\$ 43,106
Total	\$264,661

Budget Justification

Transport: Vehicles, drivers, and maintenance associated with transporting existing lab equipment and materials from the central lab to the temporary regional labs for the study, transporting the field teams to the selected Enumeration Areas in the Morogoro Region, and transporting the blood samples between the field work and the labs (regional and central labs).

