4.2 Sample Size

The sample size was determined based on the estimated prevalence, the desire precision as well as funds available, taking into account an expected maximum non-response of 70% (including refusals) at both the household and individual levels. Table 1 provides prevalence estimates for different biomarkers in Tanzania. For those biomarkers for which we do not have information, we have assumed a prevalence of 50% (most conservative approach). The sample size required for this survey is ~1170 women. This sample size takes into account urban and rural representation with 80% power, a precision of 95%, a margin of error of 5%, a design effect of 2, and a response rate of 68% (Henderson, 1982; Lemeshow, 1985; Rosenthal et al. 2017)).

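### The Wald chi-square named for contingency tables is liberal with 45 EAs: about 1.5 to 1.7 times the nominal 5% for 4- and 5-category factors region-wide, and 2 to 3 times within one stratum

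*Protocol*

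**What the plan says.** Section 4.6 of the protocol names the test: "Significance will be determined for contingency tables by Wald's X2 test". It also says "Independent variables will be analyzed as categorical variables", and that "bivariate and stratified analyses will be performed to examine the association between independent variables and deficiency status". Variables that are significant in the bivariate step then go into logistic regression models. SAS 9.4 is named and sampling weights are to be applied. The section gives no significance level for the tests, no reference distribution for the Wald statistic, no denominator degrees of freedom and no SAS procedure.

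Section 4.4 sets the design: "45 clusters will be selected from all districts (20 from urban strata and 25 from rural strata". On the second stage it says: "In the second stage, 26 households will be selected from each EA (totaling 1170 women".

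**The concern.** In a cluster survey the information about variance comes from the number of EAs, not the number of women. The Wald statistic for a table with several categories inverts an estimated covariance matrix with as many dimensions as the table has degrees of freedom. When that matrix rests on few EAs, its inverse is too large on average. Chi-square critical values are then exceeded too often, and increasingly so as categories are added. This happens even when strata, EAs and weights are all declared correctly.

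The result matters because the bivariate test is the gate to the models for secondary objective v (factors contributing to deficiency). Section 4.5 lists candidates such as wealth index, age and education that are often grouped into several levels. The screen is run for many biomarkers and factors, so a modest excess per test yields extra false candidates overall.

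**Working it through.** **The plan's own figures.** The protocol gives no type I error for this test, so the design is checked first. With the prevalence in "we have assumed a prevalence of 50% (most conservative approach" and the settings in "a margin of error of 5%, a design effect of 2, and a response rate of 68" per cent:

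- 1.96² × 0.25 / 0.05² = 384.1
- × 2 = 768.3
- / 0.68 = 1130, or 44 whole EAs × 26 = 1144
- The stated design, 45 × 26 = 1170, is exact and lies slightly above this.

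**Inputs for the size of the test.**

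- Design degrees of freedom s, from section 4.4: region 45 − 2 = 43; urban 20 − 1 = 19; rural 25 − 1 = 24.
- Table degrees of freedom: k = categories − 1, for a deficient/not deficient outcome.
- Assumed, because the protocol does not state them: a 5% level (in line with "for each biomarker prevalence will be determined with 95% confidence intervals"), factors of 4 or 5 categories, a chi-square reference, and a Wald statistic that accounts for EAs.

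**Formula.** Treat the design-based Wald statistic W as Hotelling's T² on s degrees of freedom, so that W(s − k + 1)/(ks) follows F(k, s − k + 1). With c the 5% chi-square critical value on k degrees of freedom, the true size is P[F(k, s − k + 1) > c(s − k + 1)/(ks)].

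Example, region, 5 categories: k = 4, c = 9.488, threshold 9.488 × 40/(4 × 43) = 2.206 on F(4, 40), size 8.6%.

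Example, urban, 5 categories: 9.488 × 16/(4 × 19) = 1.997 on F(4, 16), size 14.3%.

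| Setting | 2 cat. | 4 cat. | 5 cat. |
|---|---|---|---|
| Region, chi-square | 5.6% | 7.4% (1.5×) | 8.6% (1.7×) |
| Urban, chi-square | 6.5% | 11.1% (2.2×) | 14.3% (2.9×) |
| Rural, chi-square | 6.2% | 9.6% (1.9×) | 12.0% (2.4×) |
| Region, F(k, s) | 5.0% | 5.9% | 6.5% |
| Urban, F(k, s) | 5.0% | 7.2% | 9.0% |
| Rural, F(k, s) | 5.0% | 6.7% | 8.0% |

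The F rows replace c with k times the 5% critical value of F(k, s).

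**Simulation under no association.** There were 2,500 runs per setting, with 20 and 25 EAs, 30%/70% stratum weights and EA-level linearised variance. The outcome intraclass correlation was set from the planned design effect of 2: 1/(26 − 1) = 0.04 at 26 women per EA, and 1/(18 − 1) ≈ 0.06 at about 18 responders (26 × 0.68 = 17.7). Factor intraclass correlation was 0 to 0.2 and prevalence 27 to 45%.

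| Setting, chi-square reference | 4 cat. | 5 cat. |
|---|---|---|
| Region | 7.3–9.2% | 9.3–9.8% |
| Urban | 9.7–11.1% | 13.9–15.5% |
| Rural | 8.2–10.9% | 12.1–12.7% |

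The highest regional figure, 9.8%, is 1.96 times nominal.

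**After the fix.** The adjusted Wald F, W(s − k + 1)/(ks) on (k, s − k + 1) degrees of freedom, has a theoretical size of 5.0%. For 4 and 5 categories it simulated at 4.8–6.6% region-wide and 3.8–6.0% within strata. In a separate simulation with within-household weights added, the Rao-Scott F gave 3.8–6.0% for 4 and 5 categories across region, urban and rural tables.

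**Sensitivity.** Appendix 8.3 describes 55 clusters instead of 45. With 55 − 2 = 53 degrees of freedom the chi-square sizes are 6.9% and 7.8%, so the conclusion does not depend on which count is used.

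**The case against.** The strongest reply is that the protocol does not fix what does the damage. It names a Wald test but no reference distribution, and that detail may properly sit in an SAP that is not shown. An adjusted Wald F is still a Wald test and holds its level. This stands in part: Rao-Scott is not the only remedy, and the change is close to a clarification. But the sentence says X2, which points to chi-square, and an ordinary F reference still leaves 5.9–6.5% region-wide and 6.7–9.0% within a stratum.

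A reader might infer that every 4- or 5-category factor is called significant two to three times too often. The documents do not support that. The survey's stated target is the region, where all 45 EAs contribute. In theory, inflation falls below 2 times once there are 23 design degrees of freedom (4 categories) or 32 (5 categories), and the region has 43. Simulated regional rates of 11–12% can be produced, but only with prevalences of 10% or 5%; the lowest figure in the protocol's Table 1 is 23.5%.

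Urban-only and rural-only tables are also an inference. Section 4.6 plans stratified analyses to look at confounding and interaction, and names no stratifying variable. If that variable cuts across EAs, 19 or 24 degrees of freedom need not apply. Some listed factors, such as health insurance, may be binary, and those are nearly unaffected.

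Finally, the bivariate test is a screen. A falsely admitted factor still faces adjustment in the logistic model, so it is not automatically reported as a contributor.

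**Conclusion.** The point holds in a limited form. As named, the test is liberal for multi-category factors: about 7.4% and 8.6% region-wide for 4 and 5 categories (1.5 to 1.7 times nominal, up to about 2 times in simulation), and about 10 to 14% if tables are confined to one stratum. Two-category factors are close to nominal.

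These sizes rest on a 5% level, the category counts, a chi-square reference and a correctly declared design, none of which the protocol states. The theoretical figures need no assumed prevalence or intraclass correlation.

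The consequence is confined to the selection step for secondary objective v. The primary objective, deficiency prevalence with confidence intervals, does not use this test, and nothing here casts doubt on it.

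**What to change.** In section 4.6, replace the Wald X2 sentence with a design-based test that has an F reference and EA-based degrees of freedom: either the Rao-Scott F or the adjusted Wald F. State that strata, EA and the relevant sampling weight are declared, and that the same test applies to regional tables and to any stratum-specific ones. State the significance level there too.

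The cost is one sentence and a choice of software option. No data collection or sample size changes. Some borderline p-values will be larger, so a few factors may no longer pass the screen.

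### The risk factor analysis promises prevalence ratios, but its only adjusted model is logistic regression with covariates screened by bivariate significance

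*Protocol*

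**What the plan says.** All the relevant rules stand in protocol section 4.6, under Outcome Measures and Analysis.

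- **Measure:** "Risk factor analysis will be carried out to determine prevalence risk ratios (PRR), and 95% confidence intervals (CI) for single and combined deficiencies".
- **Adjusted model and entry rule:** "Independent variables that are significantly associated with deficiency status in bivariate analyses will be included in logistic regression models".
- **Purpose of that model:** "to determine the relative contribution of health services and access factors controlling for other factors".

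The same paragraph plans bivariate and stratified analyses to look at confounding and interaction, and a check for collinearity. It names no other adjusted model and does not say how a logistic fit would yield an adjusted prevalence ratio.

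The analysis serves secondary objective v in section 3, on factors contributing to deficiency. Section 4.5 names the candidate factors under a published behavioural model: enabling factors (source of care, insurance, wealth index, prenatal and periconception care, government programmes) and predisposing factors (age, education).

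**The concern.** The protocol fixes a measure on one scale and an adjusted model that reports on another. For a rare outcome the gap would be negligible, but these deficiencies affect a third to a half of women.

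Two things follow. First, the prevalence ratio is the only association measure the protocol names, so an adjusted odds ratio is easily reported or read as one. Second, confounding is usually judged by comparing crude and adjusted estimates. If the crude result is a prevalence ratio and the adjusted one an odds ratio, part of any shift comes only from the change of scale.

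The entry rule is a separate weakness. Whether a variable is significant on its own is not a test of whether it confounds another association. A variable can act on deficiency in one direction and be linked to an exposure acting in the other, so that its crude association is near zero and it fails the screen. Leaving it out then biases the estimate for the exposure. A factor that fails the screen also has no estimated contribution, although estimating relative contributions is the model's stated purpose. Intervals from the final model take no account of the selection step.

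**Working it through.** The protocol gives no figure for any association, so there is none to reproduce. The check is how far apart the two measures lie at the protocol's own prevalences.

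**Inputs.** Table 1 (section 2), Morogoro column: iron deficiency 30.3%, vitamin A deficiency 43.0%, anemia 47.3%. The true prevalence ratios (PR) of 1.2 and 1.5 are illustrative assumptions.

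**Formula.** With p0 the prevalence in the unexposed and p1 = PR × p0 in the exposed:

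OR = [p1/(1 − p1)] / [p0/(1 − p0)] = PR × (1 − p0)/(1 − p1).

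**Reading A: Table 1 gives overall prevalence P, and half of the women are exposed (assumption).** Then P = (p0 + p1)/2, so p0 = 2P/(1 + PR). For anemia at PR 1.5:

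- p0 = 0.946/2.5 = 0.3784
- p1 = 1.5 × 0.3784 = 0.5676
- OR = 1.5 × 0.6216/0.4324 = 2.16

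**Reading B: Table 1 values are used as the unexposed prevalence.** For anemia at PR 1.5:

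- p0 = 0.473
- p1 = 0.7095
- OR = 1.5 × 0.527/0.2905 = 2.72

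| Outcome (Table 1) | PR 1.2, A | PR 1.2, B | PR 1.5, A | PR 1.5, B |
|---|---|---|---|---|
| Iron deficiency, 30.3% | 1.30 | 1.31 | 1.79 | 1.92 |
| Vitamin A deficiency, 43.0% | 1.38 | 1.41 | 2.03 | 2.41 |
| Anemia, 47.3% | 1.41 | 1.46 | 2.16 | 2.72 |

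Reading A fits Table 1 better, because the table reports prevalence among all women and, when PR exceeds 1, the unexposed prevalence lies below the overall one. Reading B is the upper end.

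**What this does to the crude-to-adjusted comparison.** Take anemia under reading A with no confounding at all and a crude prevalence ratio of 1.5. The matching odds ratio is 2.16, and 2.16/1.5 = 1.44. An apparent rise of 44% would then owe nothing to confounding.

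No arithmetic applies to the entry rule. That argument rests on the stated rule set against the stated purpose of the model.

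**The case against.** An odds ratio is a valid measure and misleads only if read as a prevalence ratio. The sentence on prevalence ratios and the sentence on logistic models are separate, and nothing says that logistic output will be labelled as a prevalence ratio. Logistic regression can also deliver adjusted prevalence ratios through predicted marginals, and an analysis plan that is not shown might say so. The planned stratified analyses allow some check of confounding on the prevalence-ratio scale. On screening, the candidates come from a stated framework and collinearity will be examined, so the covariate set is not arbitrary.

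Much of this stands, and it limits the point. It rules out saying that the reported associations will be overstated. It does not remove the mismatch, since the protocol itself names a measure and an adjusted model on different scales and gives no link. Stratification handles only one or two variables at a time and does not replace the multivariable result. A sound candidate list does not cure an entry rule based on p-values.

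A reader might also infer that the confidence intervals will be too narrow. Section 4.6 says "Sampling weights will be applied and prevalence estimates will be calculated" and names no variance method, although section 4.4 states that "a stratified, multistage probability sample will be used for urban and rural areas" and section 4.2 assumes "a design effect of 2". If clustering were ignored at that design effect, interval widths would shrink by a factor of 1/√2 = 0.71 and nominal 95% coverage would fall to about 83%. The documents do not support this as a finding. They do not say that weights are the only design feature used, they neither state nor exclude a design-based variance, and the variance method is commonly left to the analysis plan. The design effect of 2 is also a planning value for a prevalence, and none is given for regression coefficients.

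**Conclusion.** The point holds for secondary objective v, in two parts.

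- **Scale.** The named measure and the only adjusted model do not match. At Table 1 prevalences a true prevalence ratio of 1.5 corresponds to an odds ratio of about 1.8 to 2.2 (overall prevalence, 50/50 exposure assumed) or 1.9 to 2.7 (unexposed prevalence). The exaggeration is conditional on an odds ratio being read as a prevalence ratio. The difficulty in comparing crude prevalence ratios with adjusted odds ratios arises however the latter are labelled.
- **Screening.** Admission by bivariate significance is a written rule. It can exclude masked confounders, and the later intervals ignore the selection. The documents give no basis for putting a size on this.

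The size of the scale gap is not known for RBC folate and vitamin B12, whose Morogoro prevalences Table 1 lists as unknown. The primary results, which are prevalences with 95% CIs, and the crude prevalence ratios are untouched. Narrow intervals are not part of this conclusion.

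**What to change.** In section 4.6:

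1. State that adjusted prevalence ratios with 95% CIs will be estimated directly, either by survey-weighted modified Poisson regression (log link, robust variance) or as ratios of predicted marginals from the logistic model. At these prevalences the second has the advantage that fitted values stay below 1. If odds ratios are wanted as well, label them as such.
2. Replace the bivariate screen with a covariate set fixed in advance from the enabling and predisposing factors in section 4.5. That list is open-ended and must be closed first. Bivariate results can still be reported descriptively.
3. As a clarification only, name urban/rural as strata, the EA as primary sampling unit, and the weight set used for each analysis.

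The cost is a few sentences, a small amount of programming in SAS 9.4, and possibly a few more model terms. The sample can carry these. If 68% of the 1,170 women give results (1,170 × 0.68 = 796), about 241 would have iron deficiency (× 0.303) and 376 anemia (× 0.473). Halved as a rough allowance for a design effect of 2, these are about 120 and 188, against the eight factors that section 4.5 names, some of which will need several categories.
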